6.8.1.2. Prohibited Non-biologic DMARDs and Apremilast

All other non-biologic DMARDs (including, but not limited to chloroquine, gold preparations, penicillamine) and apremilast must be discontinued at least 4 weeks prior to the first administration of study intervention and remain prohibited through Week 112.

6.8.1.3. Systemic Immunosuppressive Drugs

Systemic immunosuppressants (including, but not limited to azathioprine, cyclosporine, 6-thioguanine, mercaptopurine, mycophenolate mofetil, hydroxyurea, or tacrolimus) must be discontinued at least 4 weeks prior to the first administration of study intervention and remain prohibited through Week 112. If any of these systemic immunosuppressants is initiated during the study, study intervention must be permanently discontinued.

Systemic immunosuppressants do not refer to corticosteroids; see Section 6.8.2 for restrictions regarding the use of corticosteroids.

6.8.2. Corticosteroids

6.8.2.1. Oral Corticosteroids

Participants not using oral corticosteroids at baseline for PsA must have discontinued oral corticosteroids at least 2 weeks prior to the first administration of study intervention and must not receive oral corticosteroids through Week 52 of the study for PsA. An exception is made for participants who qualify for early escape at Week 16.

Participants using oral corticosteroids at baseline for PsA must be on a stable dose equivalent to \leq 10 mg prednisone per day for at least 2 weeks prior to the first administration of study intervention and continue on this dose through Week 52 unless early escape at Week 16.

After Week 24 and through Week 52, a one-time dose decrease in oral corticosteroids is allowed; otherwise, throughout the study, the dose and type of oral corticosteroid may be changed at the discretion of the investigator only if the participant develops unacceptable side effects.

6.8.2.2. Corticosteroids – Intravenous, Intramuscular, or Epidural Administration

Intravenous, intramuscular, or epidural administration of corticosteroids for the treatment of PsA are not allowed through Week 112.

Long-term (>2 weeks) oral, IV, intramuscular, or epidural corticosteroid use for indications other than PsA or psoriasis are not allowed through Week 112. Short-term (≤2 weeks) oral, IV, intramuscular, or epidural corticosteroid used for indications other than PsA should be limited to situations where, in the opinion of the investigator, there are no adequate alternatives.

6.8.2.3. Corticosteroids – Intra-articular Injection

Attempts should be made to avoid intra-articular corticosteroid injections for PsA, especially during the first 24 weeks of the study. However, if necessary, participants may receive up to 2 intra-articular, tendon sheath, or bursal corticosteroid injections in no more than 2 affected sites within any 24-week period of the study. In the case of severe tenderness or swelling in a single joint, it is suggested that the participant be evaluated for infection prior to receiving an intra-articular corticosteroid injection.

6.8.2.4. Corticosteroids – Other Routes of Administration

Inhaled, otic, ophthalmic, intranasal, and other routes of mucosal delivery of corticosteroids for indications other than PsA and psoriasis are allowed throughout the course of the study.

6.8.3. Nonsteroidal Anti-inflammatory Drugs and Other Analgesics

For participants receiving NSAIDs, including aspirin and selective cyclooxygenase 2 inhibitors, or other analgesics for PsA at baseline, treatment with a stable dose of NSAIDs or other analgesics should have been initiated at least 2 weeks prior to the first administration of study intervention and continue through Week 24 unless early escape at Week 16. The dose administered should be the usual marketed dose approved in the country where the study is being conducted.

The use of topical analgesics including capsaicin and diclofenac is allowed and should be recorded in the eCRF. For topical and analgesic patches, the dose should be stable through Week 24 and may be changed only if the participant develops unacceptable side effects.

Participants not receiving NSAIDs or other analgesics for PsA at baseline must have discontinued NSAIDs or other analgesics at least 2 weeks prior to the first administration of study intervention and must not receive NSAIDs or other analgesics for PsA through Week 24 of the study. An exception is made for participants who qualify for early escape at Week 16.

After Week 24, participants with ongoing PsA disease activity can initiate or increase the dose of NSAIDs or other analgesics based on the investigator's clinical judgment.

At any time during the study, the dose of NSAIDs or other analgesics may be reduced or temporarily discontinued due to abnormal laboratory values, side effects, concurrent illness, or the performance of a surgical procedure.

Use of NSAIDs and other analgesics for indications other than PsA are permitted throughout the study.

In this study, aspirin is considered an NSAID, except for low-dose aspirin prescribed for cardiovascular or cerebrovascular disease.

6.8.4. Biologic Agents, Cytotoxic Drugs, JAK Inhibitors, or Investigational Agents

The concomitant use of biologic agents, cytotoxic agents, JAK inhibitors, and/or investigational drugs is not allowed, with the exception of limited emergency use for treatment of COVID-19 infection. Biologic agents include, but are not limited to golimumab, anakinra, etanercept, adalimumab, infliximab, ustekinumab, alefacept, efalizumab, rituximab, natalizumab, certolizumab pegol, bimekizumab, tildrakizumab, secukinumab, ixekizumab, brodalumab, and respective biosimilars as applicable. Cytotoxic agents include, but are not limited to chlorambucil, cyclophosphamide, nitrogen mustard, and other alkylating agents. JAK inhibitors include, but are not limited to tofacitinib, baricitinib, filgotinib, peficitinib, upadacitinib and decernotinib. If any of these medications are used, study intervention must be permanently discontinued, with the exception of limited emergency use for treatment of COVID-19 infection. Continuation of study intervention in such cases should be discussed with the Sponsor's medical monitor

6.8.5. Complementary Therapies

The use of complementary therapies, including ayurvedic medicine, traditional Chinese, Taiwanese, or Korean medications or non-medicinal therapy such as acupuncture for PsA or psoriasis, is not allowed from 2 weeks prior to the first administration of study intervention through Week 112.

6.8.6. Topical Therapy and Ultraviolet B Light

Concurrent use of topical medications/treatments for psoriasis (eg, topical or intralesional corticosteroids, keratolytics (with the exception of salicylic acid shampoos, which are allowed throughout the study), coal tar (with the exception of coal tar shampoos, which are allowed throughout the study), anthralin, vitamin D3 analogues, or topical tacrolimus, and retinoids) are not permitted through Week 24.

Use of salicylic acid- and tar-containing shampoos is not permitted on the morning prior to a study visit; non-medicated shampoos may be used on the day of a study visit.

Low-potency topical corticosteroids may be used on the face and groin only. Low and mid-potency topical or intralesional corticosteroids (Class III-VII) may be used after Week 24 for psoriasis. High and ultra-high potency corticosteroids (Class I and II) are prohibited through Week 112.

Phototherapy including UVB or tanning beds are not permitted during the study through Week 112. Participants should be encouraged to avoid prolonged sun exposure during the study.

6.8.6.1. Systemic Therapy for Psoriasis

Concurrent use of systemic therapy for psoriasis (eg, psoralen with ultraviolet light A, systemic retinoids, cyclosporine or tacrolimus, with the exception of those in Table 3) must be discontinued at least 4 weeks prior to the first administration of study intervention and is not permitted during the study through Week 112; if a systemic antipsoriatic treatment (except those in Table 3) is initiated during the study, study intervention must be permanently discontinued.

Participants must not receive any biologic outside of the protocol or participate in any other clinical study with an investigational agent while in this study and must terminate study participation if they do. Prior to termination of study participation, participants should complete evaluations for a study intervention discontinuation visit.

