- d. If a participant discontinues study drug intervention prior to the Week 24 visit, they should be encouraged to return for all remaining study visits through Week 24. The participant should also return for a final safety visit to perform assessments under the Week 112/final safety visit approximately 12 weeks after the last study intervention administration. If a participant permanently discontinues study intervention administration at or after the Week 24 and before the Week 100 visit, the final efficacy visit should occur at the time of discontinuation or as soon as possible and all assessments under the Week 100/final efficacy visit should be performed. Fasting is not required for the final efficacy visit. The participant should also return for a final safety visit to perform assessments under the Week 112/final safety visit approximately 12 weeks after the last study intervention administration.
- e. Must be signed before first study-related activity.
- f. Participants with spondylitis with peripheral arthritis as their primary arthritic presentation of PsA will have confirmation of sacroilitis during screening by a centrally read pelvic X-ray (ie, anteroposterior views of the sacrum). An existing X-ray done within 3 months of screening may be sent for central reading in lieu

- of a screening X-ray (and if not of sufficient quality, a new screening X-ray would then be performed and centrally read). Participants who have confirmed sacroiliitis will complete the BASDAI at specified visits in the SoA.
- g. Study intervention will be administered SC q4w by a healthcare professional during visits to the site until the participant (or caregiver) is trained for self-administration. Study intervention will be administered by site personnel at Weeks 0 and 4. Beginning at Week 8, at the discretion of the investigator and participant, and after appropriate and documented training, participants (or caregiver) may administer study intervention at the investigative site under the supervision of a health care professional. After appropriate training, beginning at Week 32, participants (or caregiver) may administer study intervention at home and on-site visits are only required at Weeks 36, 44, and 52. Safety and efficacy assessments, including blood samples for clinical laboratory and pharmacokinetics/immunogenicity, as specified in the SoA should be performed prior to study intervention administration.

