4.4. End of Study Definition

End of Study Definition

The end of study is considered as the last visit for the last participant in the study. The final data from the study site will be sent to the Sponsor (or designee) after completion of the final participant visit at that study site, in the time frame specified in the Clinical Trial Agreement.

Study Completion Definition

A participant will be considered to have completed the main study if he or she has completed assessments at the 12-week safety follow-up visit at Week 112.

Participants who prematurely discontinue study intervention for any reason prior to Week 100 should complete the specified study visits and the final safety follow-up visit as outlined in Section 1.3 and Section 7.2. Participants will not be considered to have completed the study unless they complete the safety follow-up.

 $CONFIDENTIAL-FOIA\ Exemptions\ Apply\ in\ U.S.$

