5.3. Lifestyle Considerations

Potential participants must be willing and able to adhere to the following lifestyle restrictions during the course of the study to be eligible for participation:

- 1. Refer to Section 6.8, Concomitant Therapy for details regarding prohibited and restricted therapy during the study.
- 2. Agree to follow all requirements that must be met during the study as noted in the Inclusion and Exclusion Criteria (eg, contraceptive requirements).
- 3. Must not receive guselkumab outside of this protocol or participate in any other clinical study with an investigational agent while in this study and must terminate study participation if they do.

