- The participant has a reaction resulting in myalgia and/or arthralgia with fever and/or rash (suggestive of serum sickness and not representative of signs and symptoms of other recognized clinical syndromes) occurring 1 to 14 days after an injection of study intervention. These may be accompanied by other events including pruritus, facial, hand, or lip edema, dysphagia, urticaria, sore throat, and/or headache.
- The participant has a malignancy including squamous cell skin cancer. Consideration may be given to allowing participants who develop ≤2 basal cell skin cancers that are adequately treated with no evidence of residual disease to continue to receive study intervention.
- The participant has severe liver test abnormalities that are not transient and are not explained by other etiologies, as described in Appendix 10.8.
- The Sponsor may elect to terminate the study at any time, and if the Sponsor decides not to continue development for any reason, study medication/drug will no longer be provided to any participants.

Discontinuation of a participant's study intervention should be considered under the following conditions:

- If the participant initiates treatment with prohibited therapies, the medical monitor or designee should be notified for possible discontinuation of study intervention.
- Recurrent or chronic serious infection.
- The participant develops a serious infection, including but not limited to sepsis or pneumonia.

 Note: Any serious infection should be discussed with the medical monitor or designee, and study intervention should be withheld until the clinical assessment is complete.
- Discontinuation of study treatment should be considered for participants who report suicidal Ideation level 4 (some intent to act, no plan), Ideation level 5 (specific plan and intent), or any suicidal behavior (actual suicide attempts, interrupted attempts, aborted attempts, or preparatory actions) on a postbaseline (after Week 0) electronic Columbia-Suicide Severity Rating Scale (eC-SSRS) assessment. Discussion of such participants with the medical monitor or designee is required.
- The participant develops a severe injection-site reaction, but not meeting criteria specified above.

If a participant discontinues study intervention for any reason before the end of the study, they should be encouraged to continue in the study to complete protocol specified evaluations as outlined in the SoA (Section 1.3) and Section 7.2.

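### Protocol 6.8.6.1 ends study participation after any outside biologic, while 6.8.4 stops only study intervention and the rest of the protocol plans follow-up after a stop

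*Protocol*

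**What the plan says.** Protocol Section 6.8.6.1 is headed as a section on systemic psoriasis therapy. Its second paragraph opens "Participants must not receive any biologic outside of the protocol", adds enrolment in another investigational study, and says that anyone who does either "must terminate study participation if they do. Prior to termination of study participation, participants should complete evaluations for a study intervention discontinuation visit". It has no COVID-19 exception.

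Protocol Section 6.8.4 covers biologic agents by name, together with cytotoxic drugs, JAK inhibitors and investigational agents. If one is used, "study intervention must be permanently discontinued, with the exception of limited emergency use for treatment of COVID-19 infection". For the excepted use, "Continuation of study intervention in such cases should be discussed with" the sponsor's medical monitor. This section is silent on visits.

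Follow-up after stopping is set elsewhere in the protocol:

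- Section 4.4, which also asks for the closing safety visit: "Participants who prematurely discontinue study intervention for any reason prior to Week 100 should complete the specified study visits".
- Section 7.1, for a stop for any reason: "they should be encouraged to continue in the study to complete protocol specified evaluations as outlined in the SoA".
- Section 7.2 and footnote d of the Schedule of Activities (Section 1.3): visits encouraged through Week 24 after an earlier stop, a final efficacy visit after a later stop, and in both cases a "final safety visit to perform assessments under the Week 112/final safety visit approximately 12 weeks after the last study intervention administration".

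Section 5.3 also ends participation, but on a narrower trigger: "Must not receive guselkumab outside of this protocol or participate in any other clinical study with an investigational agent while in this study".

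**The concern.** A site whose participant starts an outside biologic finds two mandatory instructions. One takes the participant out of the study after an exit visit. The other stops the injections and leaves the participant in the follow-up that the protocol plans for everyone who stops.

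Two things depend on which instruction the site follows. The first is safety data in the 12 weeks after the last dose, which Inclusion Criterion 17 treats as the period of relevant systemic exposure. Table 1 of the protocol raises a possible added risk of infection or malignancy when guselkumab is combined with other immunosuppressive therapy. A participant who adds a second biologic inside that window is therefore one whom the safety visit should keep. The second is the Week 24 observation, which the Treatment Policy Estimand in the SAP would use whatever other therapy has been taken.

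**Working it through.** No figure in the plan is in dispute, so the check is mainly a comparison of texts.

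| Protocol section | Trigger | Action | COVID-19 exception |
|---|---|---|---|
| 6.8.6.1, second paragraph | any outside biologic, or another investigational study | end study participation after an exit visit | none |
| 6.8.4 | biologics, cytotoxics, JAK inhibitors, investigational agents | stop study intervention permanently | yes, limited emergency use |
| 6.8.6.1, first paragraph | systemic antipsoriatic treatment outside Table 3 | stop study intervention permanently | none |
| 5.3 | outside guselkumab, or another investigational study | end study participation | none |
| 7.1 | any prohibited therapy | notify the medical monitor; consider stopping study intervention | none |
| 4.4, 7.1, 7.2, footnote d | study intervention stopped | further visits and a 12-week safety visit | not applicable |

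Sections 5.3 and 6.8.6.1 agree on outside guselkumab and other investigational studies. For every other biologic, only the second paragraph of 6.8.6.1 ends participation. A biologic started for psoriasis falls under both paragraphs of 6.8.6.1, which give different actions. The withdrawal reasons in 7.2 are loss to follow-up, withdrawal of consent, death and sponsor decision; outside biologic use is not named.

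**Safety follow-up at risk.** The planned window is 12 weeks × 7 = 84 days. If the safety visit or a later contact still takes place, 0 days are lost. If the participant leaves on the day of the last dose with no later contact, 84 days are lost. The documents fix neither the timing of exit nor a later contact, so the range is 0 to 84 days per participant. Section 10.6.5 still requires unresolved SAEs to be followed and treats a death within 12 weeks of the last dose as an SAE. What can be missed is new non-fatal events.

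**Efficacy visits at risk before Week 24.** Post-baseline joint assessments through Week 24 fall at Weeks 4, 8, 12, 16, 20 and 24. After an exit at Week 4, 8, 12, 16 or 20, the number remaining is 5, 4, 3, 2 or 1. Week 24 is always among them.

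**Which analyses are affected.**

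- Treatment Policy (SAP 5.3.4.4, Supplementary Analyses 1 and 2, and the corresponding analyses of the major secondary endpoints): an observable Week 24 value becomes missing and is multiply imputed under missing at random. For ACR responses, the imputation model in SAP Appendix 12 lists the seven ACR components, intervention group and baseline non-biologic DMARD use. No listed term represents starting another biologic or stopping treatment.
- Primary analysis: a participant who stops study intervention before Week 24 because of an outside biologic meets intercurrent event 1 and is a non-responder under either section. Use after Week 24 cannot affect the Week 24 endpoint.

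**The case against.** The strongest reply is that the sponsor would resolve the matter before anything is lost. Section 6.8 requires the sponsor to be told of any prohibited therapy, in advance if possible. Appendix 10.9 says that after a positive COVID-19 test the site should discuss dosing, assessments and follow-up with the sponsor's medical officer. Section 6.8.4 is the section on biologics, and Amendment 1 added its COVID-19 exception deliberately; use that it permits can be read as not being outside the protocol. On COVID-19 this reply largely stands: the missing exception in 6.8.6.1 is a drafting gap that the sponsor would probably close case by case.

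For other biologics the reply is weaker. Notification brings the sponsor in but does not say which instruction governs. Ending participation is a different status from stopping injections, and sponsor decision in 7.2 could cover it, but that explains a withdrawal without removing the conflict with 6.8.4.

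It is also fair that some safety capture survives. Section 8.3.1 allows a later safety contact, and Section 8.4.1 plans a final serum sample for withdrawn participants. The Treatment Policy analyses are supplementary, and they have multiple imputation and a tipping-point analysis behind them. These points limit the size of the loss, but an observed value is still better than an imputed one.

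A reader might go further and infer that the primary result is distorted because a COVID-19 emergency user could continue under 6.8.4 but becomes a non-responder under 6.8.6.1. The documents do not support that as a finding. Section 6.8.4 sends continuation to the medical monitor and does not promise it. Classification as intercurrent event 1 is an inference: the SAP limits Natural Disaster to site closure, access restrictions and lockdowns, while Appendix 10.9 has sites label such discontinuations as COVID-19-related. No number of users is given.

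**Conclusion.** The conflict is in current operative text and should be corrected. For biologics other than guselkumab, 6.8.6.1 requires an exit that 6.8.4 does not require and that goes against the follow-up planned in 4.4, 7.1, 7.2 and the Schedule of Activities.

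For each affected participant, the cost is somewhere between none and all of the 84-day safety window and, for use before Week 24, one to five joint assessments at the exit weeks considered, including Week 24. Across the trial the effect is probably small, because outside biologic use is probably uncommon. That is a judgement, since neither document gives a rate. The consequence falls on new non-fatal safety events and on the supplementary Treatment Policy analyses; the primary analysis is essentially unaffected. It would also go too far to say that the safety window is certain to be lost, or that COVID-19 cases have no route to resolution.

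**What to change.** In Protocol 6.8.6.1:

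1. For outside biologics, replace termination of participation with permanent discontinuation of study intervention and follow-up per Section 7.2 and the Schedule of Activities.
2. Cross-refer to the COVID-19 emergency-use exception in 6.8.4 and to Appendix 10.9.
3. Where termination is kept, for outside guselkumab or another investigational study as in Section 5.3, still require the 12-week final safety visit or a safety contact. Otherwise the same follow-up loss remains for those participants.

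Optional tidying: say which visit in the Schedule of Activities serves as the discontinuation visit, and point the prohibited-therapy item in 7.1 to 6.8.4.

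The cost is a few words, plus a few more off-treatment visits that the Schedule of Activities already contains.
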